7.2.4 Rash

Grade 1 or 2

MVC may be continued without interruption. Subjects with a Grade 1 or 2 rash may be treated symptomatically with permitted antipyretic, antihistamine, and/or non-steroidal anti-inflammatory medications, but should be monitored closely by the local investigator.

Grade 3 or 4

A rash of Grade 3 or 4 necessitates that all MVC should be held for any Grade 3 or 4 rash unless the rash is determined to be unrelated to MVC. Upon resolution to Grade ≤ 1 , the subject should be removed from study.

7.2.5 Nausea and Vomiting

Grade 1 or 2

MVC may be continued without interruption. Subjects with Grade 1 and 2 nausea or vomiting may be treated symptomatically with permitted oral antiemetic therapies or antiemetic suppositories. Subjects should be instructed to take medications with food.

Grade 3 or 4

Subjects with Grade 3 or 4 MVC-related nausea and vomiting should interrupt MVC until the toxicity grade returns to Grade ≤ 2 or to baseline and be treated symptomatically. If Grade ≥ 3 nausea and vomiting recurs upon the resumption of MVC despite symptomatic treatment, MVC should again be interrupted and the protocol team notified for possible study discontinuation.

7.2.6 Diarrhea

Grade 1 or 2

MVC should be continued without interruption. Subjects with diarrhea of any toxicity grade may be treated symptomatically with permitted antimotility agents.

Grade 3 or 4

For diarrhea that is unresponsive to antimotility agents and for which an alternative etiology (e.g., infectious diarrhea) is not established, MVC should be interrupted until resolution of diarrhea to Grade ≤ 2 or baseline. If Grade ≥ 3 diarrhea recurs upon the resumption of study medications, MVC should be

interrupted and the protocol team should be notified for possible study discontinuation.

7.2.7 Hyperglycemia

Fasting hyperglycemia of > 110 to 125 mg/dL is considered evidence of impaired glucose tolerance. A fasting blood glucose level above 126 mg/dL is highly suggestive of diabetes mellitus. Subjects with fasting hyperglycemia may continue MVC at the discretion of the investigator, but should be discussed with the protocol team via email. A confirmatory fasting glucose must be obtained within 4 weeks and prior to the institution of medical therapy. Hyperglycemia may be treated with oral hypoglycemic agents or insulin according to standard guidelines.

7.2.8 AST/ALT Elevations

Grade 1 or 2

MVC may be continued.

Grade 3

All grade 3 or 4 elevations of AST/ALT should be discussed immediately with the protocol team via email. MVC may be continued for Grade 3 AST/ALT elevations at the discretion of the site investigator after discussion with the protocol team. Careful assessments should be done to rule out the use of alcohol, non-study medication-related drug toxicity, or viral hepatitis as the cause of the Grade 3 elevation. The possibility of lactic acidosis syndrome should also be explored.

Grade 4

MVC should be held for AST or ALT Grade 4 elevations until the toxicity returns to Grade ≤ 2 . If the Grade 4 elevation in AST or ALT recurs, MVC should again be interrupted and the protocol team notified for possible study discontinuation.

7.2.9 Creatinine Elevations

Discontinue MVC if confirmed creatinine clearance becomes < 50 mL/min. Subjects should be followed as medically indicated until the creatinine returns to Grade < 2. The protocol team should be notified within 48 hours of any permanent therapy discontinuations.

7.2.10 Anemia/Neutropenia

Subjects with Grade 3 or 4 anemia or neutropenia attributed to any of the NRTI's should have all study treatment interrupted until the abnormality returns to Grade ≤ 2 . Therapy may be resumed after the anemia or neutropenia has returned to Grade ≤ 2 using the same dual-NRTI regimen. If Grade 3 or 4 anemia or neutropenia recurs, MVC should again be interrupted and the protocol team notified for possible study discontinuation.

Subjects with anemia or neutropenia may be treated off-study with blood transfusion and/or erythropoietin (Epogen®, Procrit®) or G-CSF (Neupogen®) at the discretion of the site investigator.

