5.3 Product Supply, Distribution, and Pharmacy

5.3.1 Study Product Acquisition

Study medications will be provided by Pfizer. All other HIV medications will not be supplied by the study, but will be made available to patients via prescription at cost to the patient and/or patient's health insurance.

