5.4 Concomitant Medications

5.4.1 Required Medications

5.4.1.1 Study medications (Maraviroc)

5.4.2 Prohibited Medications

NOTE: This list applies only to MVC. Refer to manufacture's recommendations for potential drug interactions/ contraindications for background HIV medications.

- 5.4.2.1 All investigational drugs and HIV vaccines
- 5.4.2.2 The combination of efavirenz + rifampin
- 5.4.2.3 Any immunomodulators
- 5.4.2.4 Systemic cytotoxic chemotherapy
- 5.4.2.5 All herbal products, including St John's wort, should be avoided because of the unknown drug interactions between herbal products and the antiretroviral drugs used in this study.

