7 TOXICITY MANAGEMENT

Specific management of toxicity will be discussed only for the study-provided medication, MVC. The management of medication related toxicities should be undertaken by the local investigators, with guidance available from the protocol team, protocol pharmacist and pharmaceutical sponsor, to insure the optimal safety and efficacy for the individual subject.

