7.1 Commonly occurring adverse events

7.1.1 Grade 1 or 2

Subjects who develop a Grade 1 or 2 adverse event or toxicity may continue MVC without alteration of the dosage. Those subjects experiencing Grades 1 or 2 adverse events which results in discontinuation of the MVC should be removed from the study.

7.1.2 Grade 3

Management of Grade 3 toxicities should be discussed with the protocol team via email. Please refer to the subsequent sections for management of specific events.

In the event that a subject develops a **symptomatic** Grade 3 reaction considered to be **MVC-related**, the study drug should be discontinued and the subject should be followed weekly until resolution of the adverse event. Once Grade 3 is resolved the subject should be removed from study.

7.2.3 Grade 4

Management of Grade 4 toxicities should be discussed with the protocol team via email.

Subjects who develop a Grade 4 adverse event or toxicity judged to be **MVC related** will have the study drug permanently discontinued. Exemptions include: asymptomatic elevations of CPK, cholesterol or triglycerides. For these laboratories, medication may be continued at the discretion of the site investigator and laboratories repeated within 2 weeks. For other Grade 4 events, if the toxicity or laboratory elevation is thought not to be due to MVC, MVC may be continued and laboratories repeated within 2 weeks. If it is not possible for the investigator to discern the causative agent or MVC is possible/ probably the causative agent, then all MVC must be discontinued. A new regimen may be chosen at the discretion of the local investigator. Subjects experiencing Grade 4 adverse events requiring permanent discontinuation of MVC therapy should be followed weekly until resolution of the adverse event. Once Grade 4 is resolved the subject should be removed from study.

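### Section 7.2.10 implies that background NRTIs stop along with maraviroc, outside section 7's stated scope, and at Grade 4 it conflicts with section 7.2.3 on continuing maraviroc

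*Combined protocol and SAP*

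**What the plan says.** All references are to the combined protocol and SAP.

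- **Section 7.2.10, trigger and action.** The rule applies to "Subjects with Grade 3 or 4 anemia or neutropenia attributed to any of the NRTI's", who "should have all study treatment interrupted until the abnormality returns" to Grade 2 or lower.
- **Section 7.2.10, restart.** Once that level is reached, therapy may resume "using the same dual-NRTI regimen".
- **Section 7.2.10, recurrence.** If the abnormality returns at Grade 3 or 4, "MVC should again be interrupted and the protocol team notified for possible study discontinuation".
- **Section 7, opening.** "Specific management of toxicity will be discussed only for the study-provided medication, MVC".
- **Sections 5.3.1 and 5.4.1.1.** Section 5.4.1.1 names maraviroc as the only study medication. Section 5.3.1 adds: "All other HIV medications will not be supplied by the study".
- **Section 7.2.3 (Grade 4, printed under heading 7.1).** This sets aside symptom-free rises in CPK, cholesterol or triglycerides. For other Grade 4 events, "if the toxicity or laboratory elevation is thought not to be due to MVC, MVC may be continued", with laboratory tests repeated within 2 weeks.
- **Section 7.1.2 (Grade 3).** This sends the reader to the later, event-specific sections.
- **Section 4.1.4.** Every subject enters on a stable regimen containing at least two NRTIs.

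**The concern.** A toxicity rule has to tell a site which drugs to stop. Section 7.2.10 is triggered by toxicity from drugs that the study neither supplies nor counts as study medication. Its restart wording presupposes that those drugs were stopped, inside a section that says it manages MVC only. At Grade 4 it also instructs what section 7.2.3 leaves optional.

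Two things are at stake. First, the NRTIs are part of the regimen that keeps HIV RNA suppressed, and eligibility and the whole intensification design depend on that suppression. A rule that can be read as interrupting them should do so only on purpose. Second, sites that read the section differently will handle the same event differently. That would affect exposure to MVC at Grade 4, exposure to the NRTIs, and the HIV RNA and CD4 data collected around the event.

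**Working it through.** No arithmetic applies and the plan gives no figure to reproduce, so the check sets the passages side by side.

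1. **Is MVC interrupted under 7.2.10?** Yes. Sections 5.4.1.1, 5.3.1 and 7 all treat MVC as the study drug, so an instruction covering all study treatment includes it. The recurrence sentence says MVC is to be interrupted again, which presupposes that it was interrupted the first time.

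2. **Are the background NRTIs interrupted too?** Two readings are possible.
   - *Narrow (MVC only).* This agrees with sections 5.4.1.1, 5.3.1 and 7. But the NRTIs were then never stopped, and it is unclear why the restart needs to specify "using the same dual-NRTI regimen".
   - *Wide (MVC and the NRTIs).* This gives the restart phrase its natural meaning and fits the attribution of the event to an NRTI. But a section confined to MVC is then managing background drugs. The text also says nothing about the boosted protease inhibitor or NNRTI that section 4.1.4 requires alongside the NRTIs.

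   The restart phrase points to the wide reading and the scope statements to the narrow one. Nothing in the protocol settles it.

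3. **Does 7.2.10 conflict with the general rules on MVC?** This depends on the grade.
   - *Grade 3.* Section 7.1.2 defers to the specific sections, and 7.2.10 is one of them. There is no conflict.
   - *Grade 4.* Anemia and neutropenia are not among the laboratory exemptions in 7.2.3, so they fall under its provision for other Grade 4 events. If the event is attributed to an NRTI and thought not to be due to MVC, 7.2.3 says "if the toxicity or laboratory elevation is thought not to be due to MVC, MVC may be continued". Section 7.2.10 says MVC should be interrupted. Unlike 7.1.2, section 7.2.3 contains no deferral to later sections, and 7.2.10 does not claim precedence.

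4. **Are events not attributed to NRTIs left without a rule?** Not at Grade 4. Section 7.2.3 requires MVC to be discontinued when the event is MVC-related or when the cause cannot be discerned. At Grade 3, section 7.1.2 covers symptomatic MVC-related reactions and otherwise asks for discussion with the protocol team.

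5. **How many subjects could be affected?** All 30 planned subjects take NRTIs (section 4.1.4), and hematology is drawn at entry and at every scheduled visit from week 2 to week 36 (section 6.1). No event rate is given, so no expected count can be derived.

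**The case against.** The strongest reply is that a specific rule narrows a general permission. Section 7.2.3 says MVC *may* continue, while 7.2.10 says what *should* happen for one named event, so a site following 7.2.10 breaks no prohibition in 7.2.3. That is a fair reading of the Grade 4 tension, and it keeps the point from being a strict contradiction. But the protocol states no such precedence, and precedence would not settle whether the NRTIs stop.

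A second reply is that the restart phrase may mean only that MVC resumes on top of an unchanged backbone. The words do not exclude this, and it would fit the MVC-only scope. A site should not have to work it out.

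A third reply is that sections 7.1.2 and 7.2.3 ask sites to discuss Grade 3 and 4 toxicities with the protocol team by email, so doubtful cases would normally reach the team. This is a real safeguard and lowers the risk. It does not give the team a consistent text to apply.

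It is also tempting to say that the wide reading defeats the safety rationale in section 2.3, which rests on continued suppression during MVC treatment. That goes too far. Under the wide reading MVC stops together with the NRTIs, so the section does not leave MVC running while suppression is lost. Losing suppression would still matter, but not for the specific reason argued in 2.3.

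**Conclusion.** The point holds as an inconsistency in one toxicity section, in two parts. First, 7.2.10 implies that the background NRTIs are interrupted along with MVC, against the scope of section 7 and the naming of study medication in 5.4.1.1. Second, at Grade 4 only, it directs interruption of MVC for an event attributed to another drug, where 7.2.3 allows MVC to continue, and no precedence is stated.

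Three stronger conclusions that a reader might draw are not supported:

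- *That sites cannot tell whether MVC is interrupted.* The recurrence sentence shows that it is.
- *That MVC-related or unattributable Grade 4 events have no rule.* Section 7.2.3 covers both.
- *That the week 24 gene-expression result would be diluted by a definable amount.* The documents give no event rate, the interruption is temporary, and section 9.4.1.2 offers the 2-fold threshold only as an example. Off-drug week 24 samples can also arise from other interruption rules (7.2.5, 7.2.6, 7.2.8) and from section 6.2.4, which keeps subjects who stop MVC after week 4.

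The size is therefore qualitative: an event of unknown frequency in a trial of 30, governed by a rule that can be read as stopping part of the suppressive regimen. One assumption matters. The term study treatment has no formal definition, and its restriction to MVC is inferred from sections 5.3.1, 5.4.1.1 and 7, which agree with each other.

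**What to change.** Reconcile sections 5.4.1.1, 7, 7.2.3 and 7.2.10, and state two things explicitly:

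1. Whether the interruption in 7.2.10 includes the background NRTIs. If it does, the scope sentence of section 7 has to acknowledge that. If it does not, the restart wording has to change.
2. Whether 7.2.10 or 7.2.3 governs Grade 4 anemia or neutropenia that is not attributed to MVC.

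Which clinical rule to adopt is for the protocol team. The change is a rewording of one short section, with a cross-reference to 7.2.3 and possibly an adjusted scope sentence in section 7. It needs no new data, visits or subjects.

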7.2.11 CK Elevations

Asymptomatic elevations in CK or elevations due to exercise **should be repeated (within 2-4 weeks) to assure that they are transient or due to exercise and** will not require a change in study treatment. Elevations in CK $> 20 \times$ ULN should be repeated after the subject has abstained from exercise for ≥ 24 hours. For persistent CK elevations $>20 \times$ ULN should prompt a permanent discontinuation of MVC and subjects should be discontinued from study and the protocol team should be notified.

8 CRITERIA FOR TREATMENT DISCONTINUATION

8.1 Criteria for Treatment Discontinuation

- MVC drug-related toxicity (see section 7, Toxicity Management).
- Active drug or alcohol use or dependence that, in the opinion of the investigator, would interfere with adherence to study requirements.
- Requirement for prohibited concomitant medications (see section 5.4.2)
- Pregnancy or breast-feeding.

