2.2.1.2 Drug Interactions and Special Populations

In vitro studies demonstrated that MVC is principally metabolized by the cytochrome P450 CYP3A and to a lesser extent CYP2C9. As a substrate of CYP3A and P-gp MVC pharmacokinetics are modulated by inhibitors and inducers of these enzymes/transporters and a dose adjustments are required when co-administered with those drugs (see section 5.4 Concomitant Medications).

Pregnancy: There are no adequate and well-controlled studies in pregnant women. The incidence of fetal variations and malformations was not increased in embryofetal toxicity studies in rats at exposures (AUC) approximately 20-fold higher and in rabbits at approximately 5-fold higher than human exposures at the recommended daily dose. Maraviroc is a Category B drug for pregnancy (see section 4.0 Selection and Enrollment of Subjects).

Renal Impairment: The safety and efficacy of MVC have not been specifically studied in patients with renal impairment. In the absence of metabolic inhibitors, renal clearance accounts for approximately 25% of total clearance of MVC. Patients with a creatinine clearance of less than 50 mL/min who receive MVC and a CYP3A inhibitor may be at an increased risk of adverse effects related to increased MVC concentrations, such as dizziness and postural hypotension; these subjects will be excluded (see section 4.0 Selection and Enrollment of Subjects).

Hepatic Impairment: The pharmacokinetics of MVC has not been sufficiently studied in patients with hepatic impairment. Because MVC is metabolized by the liver, concentrations are likely to be increased in these patients (see section 4.0 Selection and Enrollment of Subjects).

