 - Total bilirubin $\leq 2.5 \times \text{ULN}$ (unless subject receiving atazanavir).
- 4.1.8 Females of childbearing potential must have a negative serum pregnancy test at screening and agree to use a double-barrier method of contraception throughout the study period.
- 4.1.9 Karnofsky performance score ≥ 70 .
- 4.1.10 Men and women age ≥ 18 years.
- 4.1.11 Ability and willingness of subject or legal guardian/representative to give written informed consent.
- 4.2 Inclusion Criteria (CSF Sub-Study)
- 4.2.1 Enrollment in the MVC parent protocol.
- 4.2.2 Willingness to undergo lumbar puncture.
- 4.3 Exclusion Criteria (Main Study)
- 4.3.1 Current antiretroviral regimen contains tenofovir disoproxil fumarate AND didanosine in combination.
- 4.3.2 History of chronic hepatitis C (defined as HCV antibody positive and HCV RNA detectable).
- 4.3.3 History of chronic active hepatitis B (defined as surface antibody negative, surface antigen positive and HBV DNA detectable).
- 4.3.4 Concurrent use of G-CSF or GM-CSF.
- 4.3.4 Prior or concurrent use of IL-2.

- 4.3.5 Prior or concurrent use of a CCR5 inhibitor.
- 4.3.6 Active drug or alcohol use or dependence that, in the opinion of the investigator, would interfere with adherence to study requirements.
- 4.3.7 Use of any immunomodulator, HIV vaccine, or investigational therapy within 30 days of study entry.
- 4.3.8 Use of human growth hormone within 30 days prior to study entry.
- 4.3.9 Initiation of testosterone or anabolic steroids within 30 days prior to study entry. (Exception: Chronic replacement dosages in patient's with diagnosed hypogonadism is allowed).
- 4.3.10 Evidence of splenic sequestration or suppressed bone marrow function:
 - Clinical or radiographic evidence of significant splenomegaly.
 - History of leukemia or lymphoma.
 - History of myelosuppressive chemotherapy or irradiation
- 4.4 Exclusion Criteria (CSF Sub-Study)
 - 4.4.1 Relative or absolute contraindication to lumbar puncture, such as current coagulopathy, thrombocytopenia (platelets < 50,000/ μ L), hemophilia, or use of anticoagulant medication.
- 4.5 Study Enrollment Procedures

Prior to implementation of this protocol, sites must have the protocol and consent form approved by their local institutional review board (IRB). Sites must be registered with and approved by the CCTG Data Unit. Site registration must occur before any subjects can be enrolled in this study.

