Once a candidate for study entry has been identified, details will be carefully discussed with the subject. The subject will be asked to read and sign the consent form that was approved by both the local IRB and the CCTG Data Center.

A patient identification number (PID) will be assigned to each patient screened for the study. PIDs will include a site code and three-digit extension. PIDs should not be reassigned even if the patient fails to enter the study. The PID must be included on every CRF and patient blood sample. Each site must maintain a master list of PIDs in a central location. The patient registration and inclusion/exclusion CRF will be entered into the online CCTG data system

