6.1 Schedule of Events – Clinical Evaluations

	Screening	Pre-Entry	Entry	Maraviroc Therapy Intensification (24 weeks)					Post-Maraviroc Intensificatoin	Treatment Failure, Tox or Premature D/C
	Within 30 days of entry	> 48 hrs before entry	Day 0	Week 2	Week 4	Week 8	Week 12	Week 24	Week 36	
Informed Consent	X									
Medical/Medication History	X									
Documentation of HIV	X									
Clinical Assessment / AE			X	X	X	X	X	X	X	X
Documentation of within criteria HIV RNA and CD4 prior to screen labs	X									
Complete Physical Exam			X							X
Targeted Physical Exam							X	X	X	
Start and Dispense Drug			X		X		X			
Stop and Collect Drug								X		X
Concomitant Medications	X		X	X	X	X	X	X	X	X
Adherence Assessment	X		X	X	X	X	X	X	X	X

CCTG 590
Protocol version 1.0
August 13, 2008

Schedule of Events – Laboratory Evaluations

	Screening	Pre-Entry	Entry	Maraviroc Therapy Intensification (24 weeks)					Post-Maraviroc Intensification	Treatment Failure, Tox or Premature D/C
	Within 30 days of entry	> 48 hrs before entry	Day 0	Week 2 (± 1 wk)	Week 4 (± 1 wk)	Week 8 (± 2 wk)	Week 12 (± 2 wk)	Week 24 (± 2 wk)	Week 36 (± 2 wk)	
Hematology (local lab)	X		X	X	X	X	X	X	X	X
Prothrombin time (local lab) †	X									
Chemistry / LFT (local lab)	X				X		X	X	X	X
Pregnancy test (local lab)	X	And anytime when suspected								
CD4+/CD8+ (local lab)	X		X	X	X	X	X	X	X	X
§ CD4 ≤ 350; HIV RNA ≤ 50	X									
Plasma HIV-1 RNA PCR (local lab)	X		X		X			X	X	X
Plasma for MVC levels †			X		X			X		
Extended flow cytometry & PBMC collection (UCSD lab)		X	X		X			X		
Microarray - PBMCs collection (local processing in real-time)			X		X			X		
Lumbar puncture†			X		X			X		
Plasma for storage			X		X			X	X	
Serum for storage			X		X			X	X	
Ship ambient sample for extended flow in real-time		X	X		X			X		
Ship frozen all stored PBMCs, plasma and serum									X	
HIV Resistance & Tropism testing										X

§ If available within 30 days of screen then do not need to repeat laboratory test and can use value obtained within 90 days as screen value

† Only for subjects co-enrolled in the central nervous system sub-study

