6.3.3 Medication History

At screening, a complete history or all prior antiretroviral medications will be recorded in the CRF. For all other medications, a medication history (**only of those taken within the last 30 days prior to entry**) with actual or estimated start and stop dates should be obtained and recorded in the source documents and the concomitant medication CRF, including:

- All prescription medications. Including medications taken for the treatment or prophylaxis of opportunistic infections.
- Non-prescription medications.
- Alternative therapies and/or dietary supplements.
- Allergies to any medications and their formulations must be documented.

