6.3.7 Laboratory Evaluations

For all visits record all Grade ≥ 2 laboratory toxicities on the CRFs throughout the course of the study. All values, regardless of toxicity, of specific laboratories will also be recorded on the laboratory CRF; including: wbc, neutrophil count, hemoglobin, platelets, blood urea nitrogen, creatinine, glucose, AST/ALT, alkaline phosphatase, and total bilirubin.

Any laboratory toxicities that lead to a change in treatment, regardless of Grade, must be recorded on the adverse event CRF.

Refer to the Division of AIDS Table for Grading Adult Adverse Experiences, which can be found on the CCTG website: www.cctg.ucsd.edu

Hematology:

Hemoglobin, hematocrit, white blood cell count (WBC), differential WBC, absolute neutrophil count (ANC), and platelet count will be performed in real time at the site's local laboratory.

Blood volume: 3 mL

Coagulation tests

For subjects enrolled in the CSF Sub-Study: Prothrombin time, partial prothrombin time and calculation International Ratio (INR) will be performed in real time at the site's local laboratory.

Blood volume: 3 mL

Liver & Kidney Function Tests

Total bilirubin, AST (SGOT), ALT (SGPT), and alkaline phosphatase, BUN, creatinine, electrolytes (sodium, potassium, chloride, and bicarbonate) will be performed in real time at the site's local laboratory.

Blood volume: 7 mL

Pregnancy Test

For women with reproductive potential: Urine β -HCG (urine test must have a sensitivity of ≤ 50 mIU/mL) should be done at the site's local laboratory during screening, at study entry and whenever clinically suspected.

5 ml urine

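### Section 8.1 stops maraviroc for breast-feeding, but no eligibility criterion excludes it and no screening or entry item names it, so the first dose can be given to a woman who already meets a stopping rule

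*Combined protocol and SAP*

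**What the plan says.** Section 8.1 (Criteria for Treatment Discontinuation) names "Pregnancy or breast-feeding" as a ground for stopping MVC.

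On eligibility, section 4.1 admits men and women aged 18 or over. Its one reproductive condition, the second item numbered 4.1.8, reads in part "Females of childbearing potential must have a negative serum pregnancy test at screening", and adds double-barrier contraception during the study. Section 4.3 (main-study exclusions) does not mention breast-feeding. Section 4.4 covers only contraindications to lumbar puncture.

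On procedures, section 6.3.7 calls for a pregnancy test "during screening, at study entry and whenever clinically suspected". Section 6.1 schedules a "Clinical Assessment / AE" item from entry onward and a complete physical examination at entry, which under 6.3.6 includes a review of systems. Section 6.2.1 has the first dose given and witnessed at the entry visit, after the entry blood draw. Section 6.2.9 tells sites what to do if a subject becomes pregnant and says nothing on lactation.

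**The concern.** By putting breast-feeding in 8.1, the sponsor has already decided that a breast-feeding woman should not take MVC in this study. That rule operates only once treatment has begun and only once someone recognises the condition. Unlike an adverse reaction to the drug, breast-feeding can be present before the first dose, and one question would establish it. If nobody asks, a site that follows the protocol exactly can start the drug in someone who should stop it immediately. At stake is avoidable exposure of mother and infant, plus a subject who may have to be replaced. No estimate or error rate is involved.

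**Working it through.** No figure in the plan needs reproducing; the check sets the sections side by side.

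**1. Where breast-feeding appears.** Section 8.1 only.

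**2. Where it could have been caught before dosing.**

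| Place | What it covers | Names breast-feeding? |
|---|---|---|
| 2.2.1.2 Drug Interactions and Special Populations | Pregnancy, renal and hepatic impairment, each with a pointer to section 4.0 | No |
| 4.1, second item 4.1.8 | Negative pregnancy test, contraception | No |
| 4.3 | Main-study exclusions | No |
| 4.4 | Lumbar-puncture contraindications | No |
| 6.1 | Clinical and laboratory schedules | No |
| 6.2.1 | Screening, pre-entry, entry, first dose | No |
| 6.3.2 | HIV-related medical and laboratory history | No |
| 6.3.3 | Antiretroviral and recent medication history | No |
| 6.3.6 | Examination, review of systems, signs and symptoms | No |
| 6.3.7 | Laboratory tests, including β-HCG | No |

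The β-HCG test detects pregnancy, not lactation.

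**3. Path through the protocol.** Take a woman who is breast-feeding, has a negative pregnancy test, agrees to double-barrier contraception and meets the HIV, CD4 and laboratory criteria. She satisfies 4.1 and is not excluded by 4.3, or by 4.4 if she joins the CSF sub-study. Under 6.2.1 she takes the day 0 dose. At that moment she meets 8.1.

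**4. What follows if MVC is then stopped.** Before week 4, section 6.2.3b has her replaced with no follow-up evaluations, and 8.2 discontinues her from the study. That is not the whole picture. Section 6.4 keeps safety monitoring and SAE reporting in force for 8 weeks after the last dose, whether or not follow-up visits are scheduled. Section 6.2.2 asks for evaluations as soon as possible after premature treatment discontinuation, and 6.1 has a column for them. The protocol does not fully reconcile these provisions with 6.2.3b.

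**5. Conditional illustration of exposure.** This assumes that such a subject enrols, that nobody recognises it on day 0, and that every dose is taken. Section 5.1.1 gives MVC twice daily: 2 × 7 = 14 doses a week.

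- Asked before dosing on day 0: 0 doses.
- Recognised just after the witnessed dose: 1 dose.
- Recognised at the week 2 visit (window ±1 week, 6.2.2): 14 × 1 = 14 to 14 × 3 = 42 doses.
- Recognised at the week 4 visit (±1 week): 14 × 3 = 42 to 14 × 5 = 70 doses.

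These figures describe what could happen to one such subject. They are not an expected exposure for the trial.

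**The case against.** The best case against the point has four parts.

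*Entry is a supervised clinical visit.* A review of systems, a complete examination and a clinical assessment take place around day 0, and an investigator who knows 8.1 may well notice. This stands as a mitigation. It does not close the gap, because none of these items names breast-feeding and section 4 supplies no exclusion to apply if it is noticed.

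*Breast-feeding is not a unique omission.* A reader might infer that every other stopping condition in 8.1 that can exist before dosing is screened out beforehand. The documents do not support that. Drug or alcohol use is mirrored in 4.3.6 ("Active drug or alcohol use or dependence that, in the opinion of the investigator, would interfere with adherence to study requirements"), and pregnancy is tested. But 8.1 also stops MVC when a prohibited medication is required, and several items in 5.4.2, such as herbal products or efavirenz with rifampin, are not written exclusions in 4.3. The medication history ("All prescription medications. Including medications taken for the treatment or prophylaxis of opportunistic infections", together with non-prescription and alternative products) would probably reveal them, yet it is as general an item as the review of systems. The point therefore rests on breast-feeding alone, not on a contrast with the other criteria.

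*Other study documents may cover it.* Section 4.5 says that "The patient registration and inclusion/exclusion CRF will be entered into the online CCTG data system", and that form or the consent form may ask. Neither is in the text reviewed, so actual practice at the sites cannot be judged. Even so, section 4 should agree with 8.1.

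*The exposure is hypothetical.* The documents give no sex distribution, no frequency of breast-feeding and no data on MVC in lactation. Any such woman would already have been on continuous antiretroviral treatment for at least 15 months (Schema), so MVC would add to existing drug exposure. All of this is accepted and limits the weight of the point.

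**Conclusion.** The point holds as a minor safety and consistency gap: the written eligibility rules admit, and allow day 0 dosing of, a woman to whom 8.1 immediately applies. It rests on the protocol text alone and assumes that neither the consent form nor the eligibility CRF asks the question. Probably few or none of the 30 subjects are affected. The primary endpoint, sample size, power and analyses are unchanged.

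Two stronger readings should be resisted. A reader might infer that the plan accepts continued dosing during breast-feeding; it does not, since 8.1 calls for stopping once it is recognised. A reader might also infer from 6.2.3b that an exposed subject is lost to all safety follow-up; 6.4, 6.2.2 and the premature-discontinuation column in 6.1 say otherwise.

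**What to change.** Add current breast-feeding to the main-study exclusions in 4.3. Because the CSF sub-study requires enrolment in the parent protocol (4.2.1), this covers both. Have the site confirm breast-feeding status at screening and again at the entry visit before the first dose, recorded on the eligibility CRF. Section 6.2.9 needs no change, because 8.1 already governs breast-feeding that begins on study.

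The cost is one exclusion line and one question asked twice, with no added laboratory test, visit or change to the analysis.
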